5 STUDY EVALUATIONS AND MEASUREMENTS

5.1 Screening and Monitoring Evaluations and Measurements

In addition to the measures listed below, the study database and data collection instruments will also include relevant data elements from the NINDS Common Data Elements (CDE), including elements on Demographics, Health History, Physical Exam, Treatment/Intervention Data, Protocol Experience, and Safety Data (http://www.commondataelements.ninds.nih.gov/General.aspx#tab=Data_Standards).

5.1.1 Medical Record Review

The CHOP medical record will be accessed and reviewed for potential candidates who are patients, as part of the recruitment and screening process. Non – CHOP patients will be asked to provide their relevant medical records with written HIPPA authorization from their medical facility. Screening for eligibility based on medical record review will include: date of birth and review of any significant history of orthopedic, neurologic or cardio-pulmonary conditions.

5.1.2 Physical Examination

- Physical therapy examination

- Ability to initiate pulling to stand, score of at least 1 on GMFM Item 52 (inclusion criterion).
- BSID-III, gross motor scale (inclusion criterion)

5.2 Efficacy Evaluations

5.2.1 Gross Motor Function Measure (GMFM)

The primary outcome is the GMFM-66, a Rasch-analyzed measure of gross motor function designed for children with CP.⁵⁴ Computation of the GMFM-66 score involves statistical weighting of the raw item scores for difficulty. This score will also be used with the patient's age to determine GMFCS percentile rank.⁵⁵

5.2.2 Secondary Outcomes

Postural control. Using computerized posturography, participants will sit for 3-5 ten second trials on the force platform while center of pressure data are collected. This process will be repeated in kneeling and standing positions if the participant is able to maintain these positions. Center of pressure data will be interpreted using nonlinear measures of analysis. We will also administer the Early Clinical Assessment of Balance test, which is a test designed to measure postural control in young children with physical disabilities.

Physical activity. A wireless activity monitor will be provided to the caregiver, who will be instructed on use of the monitor at home, with a goal of recording 5 total hours of the child's free play in the following week. An envelope will be provided to return the activity monitor. Amount and magnitude of physical activity will be calculated using corresponding software.

Caregiver satisfaction. One caregiver of each participant will rate their child's performance on the caregiver's self-identified goals, and the their own (caregiver's) satisfaction with the child's performance using the Canadian Occupational Performance Measure.

Child Engagement in Daily Life. One caregiver of each participant will complete the Child Engagement in Daily Life Measure to obtain a measure of the child's participation in play in daily life.

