3.1.2 Study Treatment Phase (start of the study intervention)

Children will be able to continue their outside therapies, if their families' choose to do so. Whether they reduce or continue their pre-enrollment therapy schedule, families will be asked to maintain the schedule of outside physical therapy constant throughout the treatment phase. It is anticipated that most children will be receiving early intervention therapy services in the home. Other medical care will be documented but not restricted. If parents sign CHOP's standard HIPAA authorization, we will request copies of outside therapy notes to assist with documentation of co-occurring treatments. Treatment will start within one week of Assessment 1 and will be delivered by the primary or secondary research physical therapist, both of whom will be trained using the study manual to provide each type of treatment. We will follow intent to treat procedures such that no child will be withdrawn from the study for failing to adhere to the therapy schedule. A training log will be maintained for each session. One session per week will be videotaped (if separate consent is provided) for quality control to ensure that activities between the treatments remain different and are consistent with the distinguishing characteristics.

After enrollment and the initial assessment, participants will be randomized to receive either DSM or conventional (CONV) treatment, using a randomization scheme to ensure that motor ability does not differ at baseline. Participants will also be randomly assigned to either the primary or secondary research therapist who will each provide both

types of treatments, to minimize any differences related to individual therapist. Treatment in both groups will occur at an intensity of 3 times per week for 30 minutes.

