4.2 Treatment Phase

4.2.1 Assessment sessions 1-5

- Randomization (Assessment 1 only)
- Weight
- Gross motor function (GMFM-66)
- Secondary outcomes (Postural control, physical activity, caregiver satisfaction, Child Engagement in Daily Life)
- BSID-III, cognitive scale (Assessments 1 and 5)
- Family Empowerment Scale (Assessments 1 and 5)
- Possible video or photograph

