To address Aim 2, Hypothesis 2.2 (*Participants who receive DSM treatment will demonstrate greater improvements than participants who receive CONV treatment, and the differences will be maintained at follow-up*) will be analyzed by comparing GMFM-66 outcomes between participants receiving DSM treatment and those receiving CONV treatment. Baseline characteristics in each group will be compared using two-sample tests, including t-tests, the Mann-Whitney test, and chi-square tests, as appropriate for the respective type of data. We will then use a univariate approach for comparing the two treatments using analyses of variance and covariance (ANCOVA). Measurements at 6, 12, 18 and 24 weeks, as well as at both follow-up points after treatment will be individually compared between the two treatment conditions using baseline score, cognition and caregiver self-efficacy as covariates. We will also use a multivariate approach using linear mixed effects model⁵⁹ or the Generalized Estimating Equation (GEE).⁶⁰ The advantage of using the mixed effects model or the GEE approach is that they will not drop subjects from the analysis due to not having measurement at any of the post-treatment time points. Also, such analyses will allow us to examine the between subjects effects which represent a factor with two levels (treatment conditions) and within subjects effects which represent time effects (pre and post measurements) and a time by condition interaction. The random effect model will be implemented utilizing SAS Proc Mixed and the GEE will be implemented by SAS Proc Genmod. (SAS/STAT User's Guide, 2004, Version 9. Cary, NC: SAS Institute, Inc). Cognition and caregiver self-efficacy will be included as covariates in these analyses. Two-sided p values of less than 0.05 will be considered statistically significant. Similar procedures will be used for the analysis of secondary outcomes, with appropriate tests for parametric (postural control, physical activity) and non-parametric measures (caregiver satisfaction, Child Engagement in Daily Life).

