8 STUDY ADMINISTRATION

8.1 Treatment Assignment Methods

8.1.1 Randomization

After the initial GMFM-66 score from Assessment 1 is obtained, participants will be randomized to either the CONV or DSM treatment, using a randomization scheme to stratify by baseline motor ability. This will ensure that the groups do not differ in motor ability at baseline. Participants will also be randomly assigned to either the primary or secondary research therapist who will each provide both types of treatments, to minimize any differences related to individual therapist. A blinded assessor will collect all outcomes measures. Blinding of participants to treatment group is not feasible with the proposed interventions.

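### The plan does not guarantee a baseline for home physical activity that precedes randomisation and the first treatment session

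*Combined protocol and SAP*

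**What the plan says.** Section 2.2 names physical activity at home first among the outcomes to be compared between arms. Section 4.2.1 lists it at Assessments 1 to 5, so Assessment 1 supplies its baseline. Unlike the GMFM-66, it is not measured at the visit. Under section 5.2.2 the caregiver is given a wireless monitor and aims to record 5 hours of the child's "free play in the following week. An envelope will be provided to return the activity monitor". The screening list in section 4.1 contains no monitor.

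Section 4.2.1 places randomisation at Assessment 1. Section 8.1.1, repeated in section 3.2, gives the trigger: "After the initial GMFM-66 score from Assessment 1 is obtained, participants will be randomized to either the CONV or DSM treatment". Section 3.1.2 gives the order but no interval: "After enrollment and the initial assessment, participants will be randomized to receive either DSM or conventional (CONV) treatment". On the start of treatment the same section says: "Treatment will start within one week of Assessment 1 and will be delivered by the primary or secondary research physical therapist". Both arms receive three sessions a week. Sections 3.2 and 8.1.2 say that families cannot be blinded.

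Section 6.2.2 plans two analyses of the GMFM-66. One is an ANCOVA at each time point with the baseline score as a covariate. The other is a mixed model or GEE in which pre and post measurements form the time effect, with a time-by-condition interaction. It then states: "Similar procedures will be used for the analysis of secondary outcomes", and classes physical activity with the parametric measures.

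**The concern.** A baseline covariate is safe to adjust for because randomisation cannot have influenced it. Here the recording week begins at the visit to which randomisation is tied, and it is also the week in which treatment may start. Nothing in the text requires the recording to be finished before the arm is known or before the first session.

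If knowing the arm, or having attended the first sessions, changes a child's home play or the occasions on which the monitor is worn, the baseline already contains part of the arm difference. Adjusting for it, or measuring change from it, then distorts the later comparisons. The degree of contamination would differ from child to child. No section asks for the recording dates to be compared with allocation or with the first session, so it could not be examined afterwards.

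**Working it through.** **Inputs**
- Recording window: the seven days after Assessment 1, taken as days 1 to 7 (sections 4.2.1 and 5.2.2).
- First session: day 0 to day 7 after Assessment 1 (section 3.1.2).
- Frequency: 3 sessions a week, 72 in all (sections 3.1.2 and 4.2.2).
- Precision: 17 per arm, SD 9, 95% half-width 6 (section 6.3). This concerns the GMFM-66 and is used below only for scale.

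**The plan's own figure.** Half-width = 1.96 × 9 × √(2/17) = 6.05, which agrees with the stated 6 (6.29 with the t distribution on 32 df). In SD units it is 6.05/9 = 0.67. The concern does not depend on this figure.

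**Overlap of the two windows.** If the first session is on day s (s ≥ 1), the full window days before treatment number s − 1, and the share of the window on or after treatment start is (7 − (s − 1))/7.

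| First session | Full days before treatment | Share on or after start |
|---|---|---|
| day 0 or 1 | 0 of 7 | 100% |
| day 4 | 3 of 7 | 57% |
| day 7 | 6 of 7 | 14% |

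If start days 1 to 7 were equally likely (an assumption), the mean share would be 28/49 = 57%. At three sessions a week, at most 3 of 72 sessions (4.2%) fall inside the window.

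**Position of allocation.** The text gives a trigger and an order for randomisation but no interval after Assessment 1. If randomisation takes place at the visit, as the section 4.2.1 list suggests, every baseline recording follows it. If it is held back some days, some recordings precede it. Holding it until a week's recording has been posted back would use up or exceed the one-week limit for starting treatment.

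**Effect on the analysis.** Let d be the true later arm difference, b the arm difference already present in the baseline week, and r the within-arm slope of later on baseline activity.
- ANCOVA estimates d − r·b.
- A change-from-baseline contrast, as in the time-by-condition interaction, estimates d − b.
- A comparison of later recordings without baseline adjustment estimates d.

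**Likely size of b from treatment alone.** Assume, since the documents give no figure, that the effect accrues linearly and reaches 1 SD at 24 weeks. Then b is at most 1 × 3/72 = 0.04 SD. With r assumed between 0.4 and 0.7, the ANCOVA bias is 0.4 × 0.042 = 0.02 SD to 0.7 × 0.042 = 0.03 SD, and the change-score bias is 0.04 SD. Against a half-width of about 0.67 SD (17 per arm, unadjusted), this is small.

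**The case against.** The strongest reply is that this is an unspecified sequence rather than a fixed error. Section 3.1.2 puts randomisation after the initial assessment, and physical activity is listed within that assessment. Treatment may start as late as day 7 and only 5 hours of play are sought. A site could therefore comply with every section and still record some children before the first session, perhaps before allocation. The contents of Table 1, the schedule of procedures, are not in the available text and may give finer timing. This stands. A reader might infer that no child will have a clean pre-treatment value, and the documents do not support that. They support only that none is guaranteed one.

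The second reply concerns size. Both arms receive equally intensive therapy, so b is a difference between two active treatments after at most three sessions. Under linear accrual, b of 0.2 to 0.3 SD would need a 24-week effect of 0.2/(3/72) = 4.8 to 0.3/(3/72) = 7.2 SD. A reader tempted to put the bias at 0.08 to 0.21 SD (0.4 × 0.2 to 0.7 × 0.3) would be relying on values of b that have no source and that treatment cannot plausibly produce. That also stands.

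A larger b would have to come from caregiver behaviour, which is conjecture. Section 5.2.2 does not describe caregivers choosing which hours to report. If an arm-related recording habit of size b were stable, it would also be present at every later visit. The unadjusted estimate would then be d + b, ANCOVA would give d + (1 − r)·b, and adjustment would reduce the bias. So the direction cannot be stated in advance.

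Finally, r·b describes the ANCOVA only, and section 6.2.2 does not name baseline activity itself as a covariate. This limits the formula. It does not clear the mixed model, where a change-from-baseline contrast takes in the whole of b.

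None of these replies supplies a rule that puts the recording before allocation or before treatment.

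**Conclusion.** The point holds as a gap in the design of one secondary outcome. Following the rules as written can yield a baseline recorded after allocation and partly during treatment: 14% to 100% of the window days on or after treatment start, depending on the start day, with at most 3 of 72 sessions inside. How many children are affected cannot be derived, because the interval from Assessment 1 to randomisation is not stated.

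The resulting bias is of unknown size. The part due to treatment is probably a few hundredths of an SD under the assumed linear accrual and 1 SD final effect. The part due to unblinded caregivers is unquantified and may go either way. In a trial of this size it would probably sit well inside sampling error, but it is systematic and avoidable, and a missed baseline cannot be recovered later.

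Two wider readings are not supported. The primary outcome is not affected, because the GMFM-66 score is obtained before randomisation. Nor do the caregiver ratings at Assessment 1 share the problem: section 5.2.2 gives them no following-week window, and section 3.1.2 has the initial assessment precede randomisation.

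**What to change.** Amend sections 4.1, 4.2.1 and 5.2.2 so that the baseline activity recording is complete before the arm is disclosed and before the first session. One way is to give out the monitor at the screening visit once consent is signed and collect it at Assessment 1 before randomisation. This needs enough days between the two visits, a gap the text does not state. It also needs consent in hand at screening, whereas section 8.6 lets families decide after the examination. If randomisation is instead held until the recording is finished, that must be reconciled with the one-week start rule in section 3.1.2. The recording rule for later assessments can stay as it is.

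In either case, log each child's recording dates against the dates of allocation and first session. Pre-specify a sensitivity analysis that excludes baseline recordings made after either. Report alongside it the comparison of later recordings without baseline adjustment in all children, since a contaminated baseline does not enter it.

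The cost is a short amendment and some date fields. Some monitors will go to families who are not enrolled, or there will be a delay of a few days between screening and Assessment 1 or before randomisation. Whether the existing stock of monitors would suffice cannot be judged from the documents.

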5.2.3 Weight

The child's weight will be measured at each assessment to ensure that the percent weight support during treatment sessions is accurate.

5.2.4 Bayley Scales of Infant and Toddler Development, cognitive scale

The cognition age equivalent obtained from the BSID-III will be used as a covariate as patient cognition is known to influence response to rehabilitation.^{56,57} To avoid a learning effect from repeated testing, this will be completed only every 6 months.

5.2.5 Family Empowerment Scale

One caregiver of each participant will complete the Family Empowerment Scale to obtain a measure of the caregiver's self-efficacy, also known to influence response to

rehabilitation.⁵⁸ To avoid caregivers remembering their prior responses, this will be completed only every 6 months.

5.2.6 Possible video or photograph

One treatment session will be videotaped each week to quantify participant error experience (number of falls), motor variability (time spent in one motor activity before moving to the next), and salience or motor engagement (time engaged in a dynamic motor activity) during DSM treatment, allowing evaluation of the relationship of these factors to treatment response. The videotaped sessions will also be coded for the amount of time participants spend doing activities in each of the GMFM subscales, to allow evaluation of the relationship between time spent in each activity category and outcome in each subscale. Randomly selected videos will also be used for quality checks to ensure that the two treatments remain different and consistent with the distinguishing characteristics of each group.

Occasional photographs may be taken, if separate consent is provided, for educational or scientific purposes, or as souvenirs for the children.

5.3 Safety Evaluation

Subject safety will be monitored by adverse events. Anticipated and unanticipated adverse events will be recorded to confirm that DSM treatment does not pose greater risks than current interventions.

6 STATISTICAL CONSIDERATIONS

6.1 Primary Endpoint

The primary endpoint will be the change in GMFM (Gross Motor Function Measure) from baseline to each post-treatment assessment session.

6.2 Statistical Methods

6.2.1 Baseline Data

Baseline characteristics for the total sample and by treatment group will be summarized by standard descriptive summaries (including mean, standard deviation, median, minimum, maximum and range for continuous variables and frequency counts and percentages categorical variables). We will also report the 95% confidence interval for pertinence means and proportions. Baseline characteristics in each group will be compared using two-sample tests, including t-tests, the Mann-Whitney test, and chi-square tests, as appropriate for the respective type of data.

6.2.2 Efficacy Analysis

For the analysis of Aim 1, Hypothesis 1.1 (*Gross motor ability will exceed predicted values after DSM treatment and gains will be maintained at follow-up*), GMFCS percentile ranks will be obtained after 6, 12, 18 and 24 weeks of treatment based on actual GMFM-66

scores and age, and will be compared to predicted percentile ranks based on age and initial GMFM-66 score. Mean values and 95% confidence intervals will be calculated for actual and predicted scores. Optimal treatment duration will be identified as the maximum change observed at the related time point which is maintained during the following period. If maximum change occurs after 24 weeks, this time will be considered the optimal duration. Spearman correlation will be utilized to analyze Hypothesis 1.2 (*Outcomes will be related to the amount of error, variability and engagement during treatment*), to estimate the relationship between motor improvement and the amount of motor error, variability and engagement experienced during treatment.

To address Aim 2, Hypothesis 2.2 (*Participants who receive DSM treatment will demonstrate greater improvements than participants who receive CONV treatment, and the differences will be maintained at follow-up*) will be analyzed by comparing GMFM-66 outcomes between participants receiving DSM treatment and those receiving CONV treatment. Baseline characteristics in each group will be compared using two-sample tests, including t-tests, the Mann-Whitney test, and chi-square tests, as appropriate for the respective type of data. We will then use a univariate approach for comparing the two treatments using analyses of variance and covariance (ANCOVA). Measurements at 6, 12, 18 and 24 weeks, as well as at both follow-up points after treatment will be individually compared between the two treatment conditions using baseline score, cognition and caregiver self-efficacy as covariates. We will also use a multivariate approach using linear mixed effects model⁵⁹ or the Generalized Estimating Equation (GEE).⁶⁰ The advantage of using the mixed effects model or the GEE approach is that they will not drop subjects from the analysis due to not having measurement at any of the post-treatment time points. Also, such analyses will allow us to examine the between subjects effects which represent a factor with two levels (treatment conditions) and within subjects effects which represent time effects (pre and post measurements) and a time by condition interaction. The random effect model will be implemented utilizing SAS Proc Mixed and the GEE will be implemented by SAS Proc Genmod. (SAS/STAT User's Guide, 2004, Version 9. Cary, NC: SAS Institute, Inc). Cognition and caregiver self-efficacy will be included as covariates in these analyses. Two-sided p values of less than 0.05 will be considered statistically significant. Similar procedures will be used for the analysis of secondary outcomes, with appropriate tests for parametric (postural control, physical activity) and non-parametric measures (caregiver satisfaction, Child Engagement in Daily Life).

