Determining the optimal dose of pediatric rehabilitation services for children with CP and other developmental disabilities has been identified as a national priority.⁴⁸ Yet, the majority of research in the field has not explored dose-response outcomes for various interventions. The convenient, rather than scientifically-grounded, dosing of neuromotor rehabilitation historically offered during clinical trials often limits the validity and comprehensiveness of the research findings. Investigation of treatment response over a duration long enough to reach an anticipated behavioral plateau in the early stages of scientific inquiry more adequately prepares an experimental rehabilitation treatment for Phase III efficacy evaluation.⁴⁹

Both the National Institute of Neurological Disorders and Stroke (www.ninds.nih.gov) and leaders in neurology⁵⁰ and neurorehabilitation⁵¹ suggest that early clinical trials are the appropriate stage at which to evaluate the futility of a new treatment compared to another treatment or standard of care. These data are critical in determining if and how the science should progress in a definitive Phase III trial. Dobkin further emphasizes that while “a nonactive placebo may be the only therapy in a drug trial if no standard drug therapy exists, comparing a specific rehabilitation treatment to nothing is no longer acceptable.” (2009) The intensity of treatment (minutes per week) in the proposed study will approximate the average amount of physical therapy received by young children with CP in the United States. The average amount of physical therapy is 82 (SD 60) minutes per week in the United States, and 90 (SD 60) minutes per week in the Philadelphia metropolitan area.⁵² The 90 minutes per week of either treatment in the proposed study reflects this current intervention practice. However, the wide variability in the standard

amount of services means that not all children would receive this intensity outside of the research study. This variability in current practice is a common issue in identifying “standard of care” in rehabilitation trials. However, it has been determined in gold-standard trials that matching the treatment intensity of the experimental group is the most important component of the “control” group,^{24,53} and our approach reflects this standard.

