2 STUDY OBJECTIVES

2.1 Primary Objectives (or Aims)

Aim 1. To determine the optimal treatment duration of dynamic supported mobility (DSM) treatment in infants and toddlers with cerebral palsy, between 6 to 24 weeks of treatment.

Hypothesis 1.1. Gross motor ability (measured by the GMFM-66) will exceed individual predicted values in infants and toddlers with cerebral palsy after 12, 18, and 24 weeks of DSM treatment, and gains will be maintained at 3, 6 and 12 month follow-up points.

Hypothesis 1.2. Gross motor function gains will be positively related to the amount of motor error, variability and engagement experienced during DSM treatment.

Aim 2. To determine the futility of dynamic supported mobility compared to conventional rehabilitation in infants and toddlers with cerebral palsy.

Hypothesis 2.1. The frequency of adverse events among participants who receive DSM treatment and those who receive conventional (CONV) treatment will not differ by greater than 10 percent.

Hypothesis 2.2. Participants who receive DSM treatment will demonstrate significantly greater improvements in gross motor ability (measured by the GMFM-66) than participants who receive equal amounts of CONV treatment, and these differences will be maintained at each follow-up point.

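### H1.1 sets DSM children against published curves without the CONV arm, so an excess over prediction could reflect added therapy rather than DSM

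*Combined protocol and SAP*

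**What the plan says.** Section 2.1 states Hypothesis 1.1 for the experimental arm only: gross motor ability "will exceed individual predicted values in infants and toddlers with cerebral palsy after 12, 18, and 24 weeks of DSM treatment". Section 6.2.2 gives the analysis. Actual ranks at 6, 12, 18 and 24 weeks "will be compared to predicted percentile ranks based on age and initial GMFM-66 score", and the output is described as follows: "Mean values and 95% confidence intervals will be calculated for actual and predicted scores". No test or decision rule is given. The Aim 1 duration rule follows: "Optimal treatment duration will be identified as the maximum change observed at the related time point which is maintained during the following period". CONV is not mentioned in either step.

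The abstract (Study Interventions and Measures) and section 3.1 say what the curve comparison is for: to show whether the predicted course of motor development has been altered. The abstract attaches this to DSM outcomes. Both list the comparison with CONV as a further purpose.

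On therapy received, section 1.3 says "The 90 minutes per week of either treatment in the proposed study reflects this current intervention practice", citing averages of 82 minutes a week nationally and 90 locally (SD 60 for each). Section 3.1.2 says "Children will be able to continue their outside therapies" and expects most children to be receiving early intervention at home. On the amount: "Whether they reduce or continue their pre-enrollment therapy schedule, families will be asked to maintain the schedule of outside physical therapy constant" during the treatment phase. Section 8.4.3 expects at least modest gains from either study treatment.

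**The concern.** A published curve shows how children with CP developed under whatever services they had. It does not show how these children would have done with 90 more minutes of some other therapy each week. If study minutes come on top of usual therapy, DSM children may pass their predicted ranks because they had more therapy, because they were tested repeatedly, or because they differ from the reference sample. None of these is specific to DSM.

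The CONV arm shares the study minutes and the assessment schedule, so it is the natural control for such effects, but H1.1 does not use it. At stake is the Aim 1 conclusion. DSM could be no better than CONV and the trial could still report that DSM altered the predicted trajectory. The optimal duration would then be read from change that DSM did not specifically cause.

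**Working it through.** **1. The plan's own precision figure.** Section 6.3 gives 17 per arm, SD 9 and a two-sided 95% interval of ±6 for the difference between arms.

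1.96 × 9 × √(2/17) = 6.05 (6.29 using t with 32 df). The stated figure reproduces.

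**2. Weekly physical therapy.** Study therapy in either arm is 3 × 30 = 90 minutes (section 3.1.2). Average outside physical therapy is 82 or 90 minutes (section 1.3).

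- Outside therapy fully kept, US mean: 90 + 82 = 172, and 172/82 = 2.1 times usual.
- Outside therapy fully kept, local mean: 90 + 90 = 180, and 180/90 = 2.0 times usual.
- Outside therapy fully stopped: 90.

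Section 3.1.2 permits any of these, so the net added amount is unknown and will vary by child.

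**3. Where a generic gain goes.** Let b be the gain over the curve from anything both arms share, and d the effect specific to DSM.

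- DSM actual minus predicted estimates b + d.
- CONV actual minus predicted estimates b.
- The difference between them estimates d.

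The H1.1 contrast carries b at its full size. The between-arm contrast removes it if b is equal in the two arms.

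**4. Illustration.** The documents give neither b nor the SD s of actual minus predicted, so both are assumed. The scale is GMFM-66 points, one time point is used, and d = 0. Since 6.2.2 has no decision rule, I take H1.1 as supported when the DSM 95% interval lies above zero. The chance of this is 1 − F(t₀.₉₇₅,ₙ₋₁), where F is the noncentral t distribution with n − 1 df and noncentrality b/(s/√n).

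| n, s | b = 0 | b = 1.8 | b = 3 | b = 5 |
|---|---|---|---|---|
| 17, 9 | 2.5% | 12% | 25% | 58% |
| 17, 5 | 2.5% | 29% | 64% | 97% |
| 21, 9 | 2.5% | 14% | 31% | 68% |

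With an equal b in both arms, a 95% interval for DSM minus CONV keeps its two-sided 5% error.

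**5. Cost in precision.** With n = 17 and SD 9, the one-arm half-width is 1.96 × 9/√17 = 4.28 (4.63 using t). The between-arm half-width is 6.05 (6.29), wider by √2 on the normal approximation.

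**6. Data needed.** Sections 4.2.1 and 4.3.1 schedule the GMFM-66 at the same visits without distinguishing arms. Section 5.2.1 derives percentile rank from that score and age for any participant.

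**The case against.** The strongest reply is that H2.2 already does this work. Section 6.2.2 compares the arms on GMFM-66 at 6, 12, 18 and 24 weeks, adjusting for baseline score, and percentile rank is only GMFM-66 re-expressed for age. Section 3.1 ties the Phase III decision to the CONV comparison, and section 1.3 says that the uncontrolled comparison of pilot rates does not settle futility. H1.1 as worded claims an excess over prediction, under an aim about duration, and does not say that DSM caused it.

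Much of this stands. The problem is confined to H1.1 and the duration rule, and the Phase III decision does not rest on them. It does not remove the point. The abstract and section 3.1 draw a conclusion about an altered trajectory from the curve comparison itself, and nothing makes that conclusion depend on H2.2.

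A reader might go further and infer that DSM children should be expected to exceed prediction through extra therapy. The documents do not support that. They do not say how much therapy the reference children had or what extra minutes yield. Families may reduce outside therapy. Section 6.3 takes the CONV gain of 1.8 from the published scores, so it assumes no gain above the curve. The modest gains in section 8.4.3 are not said to exceed it.

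A reader might also infer that unblinded families will adjust outside therapy differently by arm and so bias H2.2. Section 3.1.2 does not say that the choice to reduce or continue is made before allocation is known. It does ask that the schedule then be held constant, and nothing suggests a difference between arms. The intensity matching it describes concerns study treatment, not total therapy. Minutes recorded before randomisation could not reveal such drift; minutes during treatment could.

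**Conclusion.** The point holds as one of interpretation and control. As planned, H1.1 could be declared supported with no DSM-specific effect, because its only comparator is a published curve while study therapy may be added to usual therapy. A child keeping average outside physical therapy would receive about 172 to 180 minutes a week, roughly twice the usual amount. That is a permitted case, not a certainty.

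The size of the resulting bias in rank or GMFM-66 points cannot be computed from the documents. The percentages in the table depend on assumed gains, assumed SDs and an assumed decision rule, and show only that modest shared gains could matter at this sample size. Cancellation in the between-arm contrast assumes that the shared gain is the same in both arms. The change should be made, but the planned H2.2 comparison is not faulted by this point.

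**What to change.** In section 6.2.2:

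1. Compute actual minus predicted percentile rank for CONV children at every visit at which it is computed for DSM children.
2. Report the DSM-minus-CONV difference with its 95% confidence interval at each time point.
3. Base any statement that DSM altered the trajectory on that difference, and keep DSM against the curve as descriptive. Align the abstract and section 3.1 with this.
4. Show the CONV values beside the DSM values used for the optimal-duration rule.
5. Summarise outside-therapy minutes during treatment by arm, from the documentation of co-occurring treatment that section 3.1.2 already foresees. State how complete it is, since copies of outside notes depend on parental authorization.

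The cost is SAP wording, a second run of a calculation on data already collected, and one summary table. No participants or visits are added. The drawback is the wider between-arm interval. The documents give no SD on the percentile-rank scale, so its width there cannot be stated in advance.
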